#### 3.2.2. Variable (or endpoint), to be obtained for each patient, that is required to address the scientific question

The co-primary endpoints to be obtained for each patient in this study to address the scientific question are ADAS-Cog-11 score at Week 24 and ADCS-ADL score at Week 24.

#### 3.2.3. The specification of how to account for intercurrent events to reflect the scientific question of interest

Premature discontinuation from the study is the primary potential intercurrent event that could occur. The following are the possible reasons for premature discontinuation that could be related to study treatment and that require an adjustment to the imputation strategy:

- Adverse Event
- Lack of efficacy

##### 3.2.3.1. Basis for Use of the Multiple Imputation Strategy

The patterns of missing data for each primary efficacy endpoint will be presented, with the number (%) of patients in each treatment group with each pattern of missingness, as demonstrated in [Table 1](#). These data will be examined in order to determine if there was any general difference in the pattern of missing data between the treatment groups, as well as to explore the assumption of missingness at random.

**Table 1: Examples of Patterns of Missingness (Study RVT-101-3001)**

Pattern	Treatment Group	Number (%) of Patients	Baseline	Week 3	Week 6	Week 12	Week 18	Week 24
1	Intepirdine	xx (xx.x%)	X	X	X	X	X	.
	Placebo	xx (xx.x%)	X	X	X	X	X	.

Pattern	Treatment Group	Number (%) of Patients	Baseline	Week 3	Week 6	Week 12	Week 18	Week 24
2	Intepirdine	xx (xx.x%)	X	X	X	X	.	.
	Placebo	xx (xx.x%)	X	X	X	X	.	.
Etc.								

In addition, a comparison of dropout due to AE will be performed between the treatment groups, along with a graphical display of the time to discontinuation due to AE by treatment group.

A concern indicated by CHMP was relating to considerable dropout. However, the actual dropout in this study is estimated to be no higher than 11%. An examination of the patterns of missing data for the co-primary endpoints demonstrates that missing data are rare, and that collection of the endpoints was, in general, thorough, and that over 87% of patients had at least one of their Week 24 co-primary efficacy endpoints collected. Further, dropout (discontinuation) due to adverse event is estimated to be less than 4%, and dropout due to lack of efficacy less than 1%. Therefore, the overwhelming majority (~95%) of Week 24 values will either be collected or will be attributed to MAR. These outcomes reflect a high level of study oversight and management of patient visits as well as patient retention to minimize the effects of missing values on the primary targets of estimation. Further, the methods proposed for the primary analysis (MMRM) are recognized as robust under these assumptions.

Data collection beyond premature (early) discontinuation was not performed in this study, while the number of patients with missing values at Week 24 is low, patients discontinuing early did not have their later efficacy data collected. Relating to this, CHMP indicated:

- “A more appropriate primary target of estimation could make use of information observed after a patient withdrew from randomized treatment. Patients starting a new medication or have their background medication changed after withdrawal should also be followed and included in the analysis, as a comparison of treatment policies would also be of interest.”

As collection of post-drop data was not performed, the alternative option to address these missing values will be pursued. To address this situation, CHMP suggested:

- “Additionally, multiple imputation methods would be an acceptable option if no observed data after treatment withdrawal are available. For imputation of missing data, information from patients receiving placebo should be considered to avoid a potential overestimation of the treatment effect. Reason for drop-out could be used and imputations for patients withdrawing due to lack of efficacy or adverse events could be treated differently.”

Therefore, to account for the intercurrent events described above, an additional analysis via multiple imputation of those missing data for those patients experiencing certain intercurrent events (discontinuation due to AE or due to lack of efficacy) is planned. The ICH E9 Addendum indicates:

- “...for a numerical variable, experiencing an intercurrent event might be ascribed an extreme unfavourable value and a suitable summary measure selected.”

Details of the details of this additional multiple imputation strategy are provided in the following section. This analysis will be performed IN ADDITION to the final SAP.

### 3.2.3.2. Description of Additional Multiple Imputation Strategy

Missing on-treatment data for the primary endpoints will be imputed utilizing multiple imputation methods. Multiple imputation provides a useful strategy for analyzing data sets with missing values. Instead of filling in a single value for each missing value, Rubin's [Rubin 1976, Rubin 1987] multiple imputation strategy replaces each missing value with a set of plausible values that represent the uncertainty about the correct value to impute. Once a monotonic missing data pattern is established, the imputation method will specifically impute data at each time point ***based on the distribution data only from the placebo-treated patients. Thus, all Week 24 values will be imputed using only the placebo-based distribution.***

To examine the primary endpoint with a multiple imputation method that does not require the MAR assumption, a pattern-mixture approach will be utilized for the imputation. The first step will be to apply a Markov chain Monte Carlo (MCMC) method [Schafer 1997] that assumes multivariate normality will be used to impute all missing values to make the imputed (resulting) data sets have strictly monotone missing patterns. The resulting monotone missing pattern will then, in a second imputation step, be used to impute the remaining missing values; specifically, a regression-based pattern-mixture method for continuous variables will be applied.

The SAS software system will be used to perform this imputation. Because the imputation of missing data is a key aspect to the analysis of the data, explicit details regarding this imputation are provided via sample SAS code that is intended to demonstrate the application of these strategies. Variable definitions are:

- TRT=treatment group (1=Intepirdine, 0=Placebo)
- Eff1 is the first time-point for the variable score
- Eff2 is the second time-point for the variable score
- Eff\_last is the last time point for the variable score. Additional variable scores (between Eff1 and Eff\_last) would be included in this model according to the time points for collection.

The first step will be to impute partially to obtain a monotone missing data pattern. ***This imputation will be done independent of treatment.***

```
proc mi data=DATAIN out=DATAIN_MONO nimpute=100 seed=123;
  var Eff1 Eff2 ... Eff_last;
  mcmc chain=multiple impute=monotone;
run;
```

The second step will be to impute the remaining (monotone) missing data that is MAR for each of the 100 imputed datasets from the first step. ***This step will assume that the distribution of missing values are based on the distribution of placebo outcomes ONLY*** (and thus reduces the risk of overestimating the treatment effect).

Ratitch and O’Kelly ([Ratitch 2011](#)) describe an implementation of the pattern-mixture model approach that uses a control-based pattern imputation. That is, an imputation model for the missing observations in the treatment group is constructed not from the observed data in the treatment group but rather from the observed data in the control group. This model is also the imputation model that is used to impute missing observations in the control group.

Following the imputation of the data to create a monotone missing pattern, missing values for the earliest missing value (visitnum1) are imputed BY VISIT. The first visit to be imputed would be the Week 3 time-point, then the Week 6, Week 12, Week 18, and finally Week 24. The Week 24 time-point is the key timepoint of interest.

The process is repeated sequentially, ie, by visit, until the monotone missing data pattern is completely filled in (imputed), and thus there may be up to 5 calls to the PROC MI procedure to generate the final imputed dataset.

The following sample SAS code demonstrates the general methodology for imputing the first visit (Week 3), second visit (Week 6) data, and third visit (Week 12). Note that the output dataset from the first imputation is used as the input dataset for the second imputation, and the output dataset from the second imputation is used as the input dataset for the third imputation. Note that minor alterations to the SAS code may be performed.

```
**First procedure imputes missing values for the first visit (Week 3);
proc mi data=DATAIN_MONO out=DATAREG1 seed=465 nimpute=1;
  class trt;
  monotone regression(eff1);
  mnar model (eff1 / modelobs=(trt='0')); **indicates only observations
  where treatment was "placebo" are used to derive the imputation model
  for the outcomes;
  var eff1;
run;

** Second procedure imputes missing values for the second visit (Week 6)
proc mi data=DATAREG1 out=DATAREG2 seed=465 nimpute=1;
  class trt;
  monotone regression(eff2);
  mnar model (eff1 eff2 / modelobs=(trt='0')); **indicates only
  observations where treatment was "placebo" are used to derive the
  imputation model for the outcomes;
  var eff1 eff2;
run;

** Third procedure imputes missing values for the Third visit (Week 12)
proc mi data=DATAREG2 out=DATAREG3 seed=465 nimpute=1;
  class trt;
  monotone regression(eff3);
  mnar model (eff1 eff2 eff3 / modelobs=(trt='0')); **indicates only
  observations where treatment was "placebo" are used to derive the
  imputation model for the outcomes;
  var eff1 eff2 eff3;
run;
```

This process is continued for all visits through Week 24.

Note that the regressions do not include the subset of observations from the Intepirdine treatment arm. **The imputed data at each time point will be based on the distribution data only from the placebo-treated patients**, and thus information only from patients receiving placebo are considered to avoid potential overestimation of the treatment effect. This is consistent with the CHMP advice:

- "... multiple imputation methods would be an acceptable option if no observed data after treatment withdrawal are available. *For imputation of missing data, information from patients receiving placebo should be considered to avoid a potential overestimation of the treatment effect. Reason for drop-out could be used and imputations for patients withdrawing due to lack of efficacy or adverse events could be treated differently.*"

However, as suggested by CHMP, for those patients discontinuing due to either AE or to lack of efficacy, imputation is treated differently. This is also specifically suggested in the ICH E9 Addendum, "...for a numerical variable, experiencing an intercurrent event might be ascribed an extreme unfavourable value and a suitable summary measure selected." This will be accomplished with an additional imputation step, as described in the following section.

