### 3.2.3.3. Imputation for Intercurrent Events of Discontinuation due to AE or Lack of Efficacy

For patients with intercurrent events of discontinuation due to adverse event OR due to lack of efficacy, imputation will follow the same strategy as above, with the difference that the imputed Week 24 values (after following the steps in the section above) will be adjusted and therefore ascribed an extreme unfavourable value.

Specifically, for these patients who discontinued due to adverse event or due to lack of efficacy at Week 24, the missing values will be scaled to "worse" as compared to patients with MAR Week 24 data. Ie, a scalar value of 10% worsening, using a patient's baseline to define the 10% scalar value, will be added to the patients Week 24 imputed value in order to 'worsen' the outcome.

The scalar will be determined as follows. Patients are expected to have an average ADAS Cog 11 score of ~25, and thus a 10% worsening would average approximately 2.5 points. Worsening of 2.5 points in the ADAS-Cog 11 was similar for the placebo arms in those clinical trials for many approved drugs (eg, donepezil, rivastigmine, memantine), and thus 10% of a patient's baseline value is a clinically relevant and meaningful adjustment (worsening) to the patients who discontinued due to adverse event or due to lack of efficacy.

For example, assume a patient discontinues prematurely due to an adverse event and the patient is therefore missing the Week 24 ADAS Cog 11 value. Imputation of missing values for this patient will be performed as follows:

- The patients missing values after discontinuation will *FIRST* be imputed accorded to the same procedures as for all patients with missing values.
- Then, the Week 24 imputed value will be *FURTHER* scaled (worsened) as follows:
  - The patients baseline value for the variable will be identified (eg, assume the patient has an ADAS Cog 11 score of 27 at baseline). And note that increases in the ADAS Cog-11 indicate a worsening of function, and thus increases from baseline would indicate a poor treatment outcome.
  - The baseline score will be multiplied by 10%, eg,  $27 * 0.1 = 2.7$ . This 2.7 would be this individual patients' scalar adjustment to the Week 24 ADAS Cog 11 score.

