  - Therefore, the imputed Week 24 score for that patient will be *increased (worsened) by 2.7*. Thus, if, for example, the patients Week 24 value is imputed by the primary imputation methods to be 25, *a further scalar increase of 2.7 will be attributed for that patient*, ie, the resulting imputed score for analysis for that patient will be  $25+2.7 = 27.7$ .

Thus, in this manner, patients who discontinue due to adverse event or due to lack of efficacy will, as a group, have a worse distributional outcome for each co-primary endpoint than other patients with missing values at random. A 10% worsening in the co-primary endpoints is considered sufficient to ensure that these patients who discontinued due to adverse event or due to lack of efficacy are treated accordingly with unfavorable outcomes.

**3.2.4. The population-level summary for the variable which provides, as required, a basis for a comparison between treatment conditions**

The population-level summary for the co-primary variables in this study are ADAS-Cog-11 score change from baseline to Week 24 and ADCS-ADL score change from baseline to Week 24. The basis for the comparison will be made using the Randomized population and the MMRM analysis on the imputed dataset that specifically attributes distributionally ‘worse’ outcomes to those patients with an intercurrent event of dropout due to either adverse event or lack of efficacy.

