#### 4. ANALYSIS POPULATIONS

The Intent-to-Treat (ITT) Population was defined as:

- All subjects randomized to treatment who have taken at least one dose of double-blind investigational product and who have at least one baseline (and one post baseline) primary efficacy assessment for at least one of either the ADAS-Cog-11 or the ADCS-ADL. This will be the primary population used for the efficacy analysis.

Note that the inclusion of ‘and one post baseline’ assessment was added to the original definition.

The Randomized Population was defined as all patients who are randomized.

CHMP advice suggested the following:

- “With regard to the definition of the ITT population, it is considered that the Intention-To-Treat population, as the definition already suggests, should consist of all patients randomized and the Applicant will have to justify that their definition (all randomized who took medication with one post-baseline assessment) will lead to the same conclusions on treatment effects.”

Therefore, an analysis of the **Randomized Population** will be performed for the co-primary endpoints using the multiple imputation strategy as indicated above, and the responder analyses as described for those outcomes.

A comparison of the conclusions regarding treatment effect between the Randomized Population and the ITT population will be performed. This analysis comparison will allow for justification as to whether the ITT population (as defined) leads to the same conclusions from the Randomized population.

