## 5. DESCRIPTIONS OF ADDITIONAL STATISTICAL ANALYSES

The key analysis method of these additional imputed data (as described in the previous sections) will be using the mixed model repeated measures (MMRM) approach. A summary of this method is described below.

Treatment comparisons between the intepirdine and placebo groups in ADAS-Cog-11 and ADCS-ADL change from baseline to Week 24 will be analyzed for the dataset using a mixed model for repeated measures with restricted maximum likelihood estimation, an unstructured covariance matrix, and the Kenward-Roger approximation for denominator degrees of freedom.

The same procedures for analysis of the imputed data (as were proposed in the original SAP) would then be performed, as follows:

- Each of the 100 imputed datasets will be analyzed using the MMRM model. The statistical model will be fitted with terms for treatment group, visit, treatment by visit interaction, baseline score, baseline MMSE, baseline score by visit interaction, and Region. In this way, the test of the efficacy endpoint at Week 24 will be obtained once for each of the 100 imputed datasets.
- The 100 resulting treatment effect parameters and standard errors from these will be combined to provide a distribution of parameters (and standard errors) upon which the sensitivity analysis will be concluded. PROC MIANALYZE will be used for this summary of the analysis.

Inferences will be drawn from treatment differences for the changes from baseline derived from the MMRM models at Week 24. As additional supportive information, treatment differences for each post baseline visit will also be derived. The estimated treatment difference for “intepirdine 35mg – Placebo” at each visit will be displayed in the summary of statistical analysis together with the 95% confidence interval and the associated p-value.

Least Squares Means for each visit will also be presented with the standard error and the number of subjects contributing to the Least Squares Means. Least Squares Means and estimated treatment differences for each visit and the associated 95% confidence interval will be displayed graphically.

Note that while the primary determination of the effects of treatment will remain based on the indicated analyses in the final SAP (August 9, 2017), comparison of those outcomes to the additional analyses above will be made to assess the robustness of the outcomes.

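### The additional placebo-based imputation omits the baseline score, so patients never assessed on a scale after baseline get Week 24 values unrelated to their own baseline

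*SAP*

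**What the plan says.** SAP addendum Section 3.2.3.2 describes two steps. The first is an MCMC step that makes the missing-data pattern monotone, with the variable list "var Eff1 Eff2 ... Eff_last". The second is a series of placebo-only regressions. The comment on the first of these reads "First procedure imputes missing values for the first visit (Week 3". That call contains eff1 alone, and each later call adds only the preceding post-baseline scores. The text lists Weeks 3, 6, 12, 18 and 24 and allows up to five calls.

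Section 3.2.3.3 then adds 10% of the patient's own baseline for those who stop because of an adverse event or lack of efficacy. For them, the "imputed Week 24 values (after following the steps in the section above) will be adjusted and therefore ascribed an extreme unfavourable value".

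Section 5 analyses change from baseline with "terms for treatment group, visit, treatment by visit interaction, baseline score, baseline MMSE, baseline score by visit interaction, and Region". Section 3.2.4 gives the analysis its role: "The basis for the comparison will be made using the Randomized population and the MMRM analysis on the imputed dataset". Section 4 uses it to check whether the ITT definition leads to the same conclusions as all randomised patients. Section 5 also says that, "while the primary determination of the effects of treatment will remain based on the indicated analyses in the final SAP", the new results are compared with those outcomes for robustness.

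**The concern.** The imputed variable is a raw score, and the analysed variable is that score minus baseline. If the imputation ignores baseline, a patient with nothing observed after baseline gets a Week 24 score centred on the placebo mean, whatever the starting severity. The implied change is then mostly the distance between the patient's baseline and the trial mean. Severe patients appear to improve sharply and mild patients appear to worsen sharply.

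This falls on the patients the analysis was added for. Those with no post-baseline score are among the patients who separate the Randomized Population from ITT. A patient can also be in ITT with a "primary efficacy assessment for at least one of either the ADAS-Cog-11 or the ADCS-ADL", and is then affected on the other scale. Section 3.2.3.1 states that "patients discontinuing early did not have their later efficacy data collected", so these values rest wholly on the imputation model. The Wilcoxon analysis in Section 5.1 uses the same 100 datasets.

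**Working it through.** **1. Is baseline one of the Eff variables?** No. The five visits (Weeks 3, 6, 12, 18, 24) match the five calls, with eff1 as Week 3. Table 1 of the addendum shows Baseline as a separate column.

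**2. Does baseline enter through a change score?** No. The worked example in Section 3.2.3.3 imputes a raw score: 27 x 0.1 = 2.7 and 25 + 2.7 = 27.7, which reproduces the plan's figure. The 2.7 is added after the draw. It does not condition the draw.

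**3. Inputs.** From the documents:
- mean ADAS-Cog-11 baseline about 25 (SAP addendum 3.2.3.3)
- SD of change 6.5, planned difference 1.6 and 575 per arm (Protocol 10.2 and Summary)
- drop-out at most 11% (SAP addendum 3.2.3.1)

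Assumed, because the documents do not give them:
- baseline SD 8 to 10
- within-visit SD 2.7
- placebo decline m of 0 to 2.5
- share never assessed 1 to 3%

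**4. One patient: never assessed, stopped for an adverse event or lack of efficacy, baseline b.**

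As written, expected change = 25 + m + 0.1b - b.

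With baseline in the model, expected change = m - (1 - k)(b - 25) + 0.1b, where k = 1 - 2.7²/SD². This gives k = 0.886, 0.910 and 0.927 for SD 8, 9 and 10.

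| Baseline | As written | Baseline in the model |
|---|---|---|
| 15 | +11.5 to +14.0 | +2.2 to +5.1 |
| 25 | +2.5 to +5.0 | +2.5 to +5.0 |
| 35 | -6.5 to -4.0 | +2.4 to +5.3 |
| 40 | -11.0 to -8.5 | +2.3 to +5.4 |

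As written, the sign turns to improvement above b = (25 + m)/0.9, that is 27.8 to 30.6. At baseline 35 the chance that the penalised value shows improvement is 64 to 75%, against 21 to 36% with baseline included.

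**5. Spread.** If change is independent of baseline, the SD of the implied change without the penalty is √(SD² + SD² + 6.5²). This is 13.1 for SD 8 and 15.6 for SD 10, against 6.5 when baseline is used.

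**6. Trial level, by simulation.** Settings: 575 per arm, true effect -1.6, five visits, placebo decline 1.25, 11% monotone drop-out, and the penalty for 5/11 of drop-outs. Imputation was placebo-only, with 25 imputations. Week 24 ANCOVA on baseline stood in for the MMRM, with Rubin's rules.

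*Balanced loss.* Bias is within 0.004. The ratio of standard errors, without to with baseline, for SD 8, 9 and 10 is:
- 1% never assessed: 1.018, 1.023, 1.029
- 3% never assessed: 1.048, 1.062, 1.079

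*Unbalanced loss.* The shift is about -0.9 x (pA·dA - pP·dP), where p is the share never assessed in the active (A) or placebo (P) arm and d is their mean baseline minus the trial mean. Negative favours the drug. Simulated shifts for SD 9 (Monte Carlo SE at most 0.003):

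| Scenario | 1% | 2% | 3% |
|---|---|---|---|
| Equal loss, active 5 points more severe | -0.045 | -0.097 | -0.129 |
| Equal loss, active 5 points less severe | +0.047 | +0.100 | +0.140 |

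For SD 8 and 10 the first row runs from -0.043 to -0.050 at 1% and from -0.124 to -0.133 at 3%. With 3% lost on active and 1% on placebo, the shift is -0.003 if their baselines are average and -0.081 if both groups are 5 points more severe.

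**7. Cross-check.** A simpler one-visit simulation (SD 10, no other drop-out) gave the same pattern. With balanced loss the standard error rose from 0.386 to 0.400 at 1% and from 0.388 to 0.416 at 2%. With active-arm losses 1 SD (10 points) worse, the shift was about 0.10 at 1%, as 0.01 x 10 predicts.

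**The case against.** The code is labelled as a sample, and Section 3.2.3.2 allows small changes to it, so adding baseline could be called permitted. The final SAP of August 9, 2017 is not available here. The CHMP advice says that plan's own multiple imputation used covariates. These points limit certainty about what would be programmed, but they do not supply the missing commitment. The addendum offers the code as the detailed specification, and none of its prose names a covariate.

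The stronger objection is about size, and much of it stands. Errors for mild and severe patients cancel on average. If drop-out were even over time, loss before Week 3 would be about 11% x 3/24 = 1.4%, so 3% is a high case. At 1% never assessed, about 575 x 0.01 x 5/11 = 2.6 patients per arm would be both never assessed and penalised. With typical baselines (SD 9), only about 0.35 of them would exceed a baseline of 35. Nothing in the documents predicts a baseline imbalance among early losses, and a larger standard error is conservative. The penalty still makes these patients worse as a group than other missing patients, which is how Section 3.2.3.3 words its aim. No planned responder analysis uses the imputed values, so the chances of apparent improvement in step 4 only illustrate the problem.

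This argues for a modest rating. It gives no reason to leave out a predictor that the analysis model already contains.

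**Conclusion.** The concern holds. As specified, the imputation does not condition on baseline for patients with no post-baseline score on a scale. For more severe patients this can turn the intended unfavourable value into an apparent improvement. Patients with some post-baseline data are conditioned on those scores and are much less affected.

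At trial level the effect is small to moderate. With balanced loss there is a loss of precision and no bias. Bias arises only if the baseline severity of early losses, weighted by their number, differs between arms. In the scenarios shown it reaches about 0.13 to 0.14 points in either direction, or 8 to 9% of the planned 1.6. These sizes rest on the assumed baseline SD, placebo decline and share never assessed. They were worked out for ADAS-Cog-11 only; the same mechanism applies to ADCS-ADL.

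Because the analysis is supportive, this should be fixed but does not threaten the primary determination.

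**What to change.** Put the baseline score of the same scale first in the variable list of the MCMC step and of every regression call (for example `var base eff1`, then `var base eff1 eff2`). Keep the placebo-only restriction. Preferably add the other covariates of the analysis model, baseline MMSE and Region indicators. State this in one sentence of Section 3.2.3.2. Report, by arm and by scale, how many randomised patients have no post-baseline value, with their mean baseline.

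A minor code correction: the regression calls lack a BY statement on the imputation number, although the text says the step is run for each of the 100 datasets. In simulation this changed the standard error by about 0.15% (0.3949 versus 0.3955).

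The cost is a few lines of code before unblinding. No new data are needed: Protocol 8.1 and Table 2 place both scales at Visit 3, before the first double-blind dose.
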